We will post information about the trial along with contact information on our website www.bionicpancreas.org and on www.clinicaltrials.gov. We will consider include subjects who did not participate in the Multiplex Pharmacokinetic study in the “different PK group” if there is data from another source suggesting that they may have differences in PK with different insulins or they have high titers of anti-insulin antibodies, which we have previously found to correlate with slow PK for insulin analogs. We will consider including subjects who did not participate in the Multiplex Pharmacokinetic study in the “same PK group” if they have normal titers of anti-insulin antibodies.

IV. Subject Enrollment

IV. a. Number of Subjects

Four subjects will complete the Test Run period. It is expected that we will have up to 30 subjects complete the RCT portion of the study with a consistent protocol for a total of up to 34 subjects. We expect that the experiments and analysis can be accomplished over a period of 6-12 months. Up to 45 subjects will be enrolled. The upper bound is based on the expectation that some volunteers will be excluded after the screening visit and the possibility that some experiments may have to be discontinued before completion (due to, for instance, intercurrent illness or subject withdrawal).

For each subject there will be an adult who lives with them who will also be considered a participant in the study. They will receive some training regarding treatment of hypoglycemia and will consent to be a designated contact for the study participant. Up to two individuals may share this role, but they must be willing to carefully coordinate with each other and the subject so that one of them is clearly designated as having this responsibility at any given time, both must consent, and both must complete the required training. These designated contacts are also enrolled in the study, bringing the total enrollment to as many as 135 subjects.

Study staff will make alternative arrangements for any subject that is unable to identify a designated contact to ensure the safety of the subject throughout the duration of the study.

IV. b. Enrollment and Consent Procedures

Prospective participants and designated contacts will be briefed by a study staff member by phone or e-mail regarding the study procedure and the inclusion and exclusion criteria. Potential subjects will be sent an informed consent document by mail, fax, or e-mail.

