V. d. ii. Randomization of Study Visit Order

Once the subject has been enrolled and eligibility of subjects has been established, subjects will be randomized to one of the possible three visit orders. The Test Run period is not randomized; all subjects will only use the insulin-only iLet with BC222 lispro.

V. d. iii. General Study Policies for all Study Arms (including the Test Run):

- Subjects will remain within a geographic boundary established based on 250 miles from the designated base for study personnel at all times and will avoid any air travel.
- If the subject is sleeping at home, the designated contact (or one of the designated contacts, if two individuals are sharing the job) must also be at home. If the subject is traveling within the geographic boundary, the designated contact must go with them.
- Subjects and their designated contact will keep a charged mobile phone on their person (or at their bedside) at all times and will answer calls from the study staff.
- Study subjects will keep a Contour Next One glucometer easily accessible at all times in case a calibration is needed, and they will do all calibrations with this meter. They will keep a glucometer, fast-acting carbohydrates, and a glucagon emergency kit easily accessible at home in case their designated contact needs to use it.
- Subjects should use the study provided Contour Next One glucometer for all BG checks throughout the study. They are encouraged to check their BG at least four times a day, before meals and before bedtime. They will also be encouraged to check before exercise and at intervals during exercise, and for any symptoms of hypoglycemia. There are no restrictions on additional checks and subjects should check as often as they wish to confirm the accuracy of the Dexcom CGM and for safety.
- Subjects will wear leur-lock compatible infusion sets throughout the study.
- Subjects and their designated contact will not use any recreational drugs or drugs of abuse, other than alcohol. The need to take prescription drugs that dull the sensorium, reduce sensitivity to symptoms of hypoglycemia, or hinder appropriate decision-making may be grounds for exclusion from the trial or discontinuation of participation, a decision that will be made by the principal investigator.

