- All study devices, including the iLet BP and the study glucometer will be downloaded. The memory of the BP will be wiped and it will be re-initialized for the next study period. Diagnostics will be performed to ensure that the Dexcom CGM device is appropriately calibrated and that all of the components of the bionic pancreas are in good communication with each other.
- Used and unused insulin vials will be returned to prevent the subject from using the wrong insulin during the wrong week.
- Anti-insulin antibody and plasma blood samples will be collected.
- Subjects will have the option to begin the next arm of the study on the same day they complete the previous study arm.
 - If subject choose this option, they will start over with Day 1 procedures:
 - If the Dexcom CGM has not already been replaced, it will be replaced at this time.
 - Study staff will provide supplies, including the next week's insulin, and review the study procedures.
 - Study staff will supervise the setup of the iLet and infusion set. Participants will need to fill the iLet with a new reservoir and place a new infusion set at the start of each new study arm.
 - Study staff will start the bionic pancreas and will verify that data streaming is working prior to the subject leaving the Diabetes Research Center.
 - If subjects choose to not continue directly to the next arm of the study, the Dexcom CGM sensor will be removed, all bionic pancreas infusion sites will be removed, subjects will put their own pump back on, and they will be discharged.
 - A provider (MD or NP) will review the last several hours of insulin dosing and assist the subject in resuming their usual care.
 - The next arm of the study will be scheduled to begin up to 14 days from the end of the previous study arm.

Final Day 7 Visit:

- At the end of the 7-day period, subjects will return to the clinic and answer the post questionnaires for the study arm.

- The body weight of the subject will be documented
- Any changes to medications or medical history and any adverse events that may have occurred since the last study visit will be documented
- Anti-insulin antibody and plasma blood samples will be collected
- The Dexcom CGM sensor and all bionic pancreas infusion sites will be removed.
- All study devices, including the iLet BP and the study glucometer will be downloaded.
- Used and unused insulin vials will be returned.

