- Usage of CGM (type of CGM, days per month worn, usage of data, whether insulin is dosed based on CGM alone, alarm settings)
- Height and weight
- Blood pressure
- EKG if applicable
- Hemoglobin A1c
- Anti-insulin antibody titers
- Plasma, for future insulin antibody assays
- Urine HCG (pre-menopausal females)
- eGFR

VI. a. 2. All Study Arms (including the Test Run period):

- CGMG (CGM glucose) every five minutes from the Dexcom CGM
- All fingerstick BG measurements taken by the subject (meter download)
- Insulin total daily dose from bionic pancreas download
- Timing of meal announcements and size of meals announced from bionic pancreas download

- Day, time, fingerstick BG measurements, CGMG readings, and insulin doses from each meal challenge
- Time subjects were not under bionic pancreas control
- List of technical faults associated with the bionic pancreas including cause and resolution
- Body weight after each study arm
- Anti-insulin antibody titers and plasma after each study arm
- Date of last menstrual period
- Information collected from the daily email survey and phone calls including but not limited to hypoglycemia, carbohydrate interventions, any nausea and/or vomiting, any other adverse events, time spent exercising each day, exercise intensity, and exercise exposure (time X intensity), any unscheduled infusion set changes or Dexcom CGM sensor changes, and alcohol intake.
- Data from questionnaires about attitudes and expectations regarding the bionic pancreas at baseline and on day 7 of each arm (RCT portion the study only).

VI. b. Study Endpoints

Statistical comparisons will be made between insulin analogs within a single participant. Three pairwise comparisons will be made between arms.

Data from the uncontrolled Test Run period will be reviewed to verify safety before proceeding with the RCT portion of the study. Descriptive statistics will be compiled based on the same analyses planned for the RCT portion of the study but no formal statistical analyses will be done. This period has no control and is intended to verify the iLet with BC222 lispro is safe and operating as expected prior to initiating outpatient experiments in a larger cohort.

VI. b. 1. Co-Primary endpoint analyses

The co-primary outcomes will be mean CGMG and fraction of time spent with CGMG <54 mg/dl.

VI. b. 2. Secondary endpoint analyses

Secondary analyses will include:

- Fraction of time spent within each of the following ranges:
 - < 50 mg/dl
 - < 60 mg/dl

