 - < 70 mg/dl
 - 70-120 mg/dl
 - 70-180 mg/dl
 - >180 mg/dl
 - >250 mg/dl
- Within day coefficient of variation (CV)
- Mean postprandial excursion (difference in CGMG from the beginning of the meal challenge to the peak CGMG in the 4 hours after the meal) for both mixed meal challenges
- Number of symptomatic hypoglycemic events per day
- Grams of carbohydrate consumed to treat hypoglycemia per day
- TDD of insulin

VI. b. 3. Other Outcomes

- Mean number of meal announcements per day
- CGM Reliability index, calculated as percent of possible values actually recorded by CGM
- CGM MARD from Dexcom G5 CGM versus time-stamped BG values from meter downloads (any other BG values will not be considered)
- Percentage of days with mean CGM glucose < 154 mg/dl (estimated average glucose corresponding to

an A1c of 7%)

- Mean postprandial AUC (4 hours following each meal challenge) for both mixed meal challenges
- Mean number of daily BG measurements
- Number of severe hypoglycemic events (subject unable to self-treat, requiring the assistance of another person)
- Mean daily basal insulin dose
- Mean daily bolus insulin dose
- List of technical faults associated with the bionic pancreas including cause and resolution

The primary analysis of the designated endpoints will be calculated on an intention-to-treat basis. In cases where an arm was not completed we will use the available data from that arm in the data analysis. We will calculate percentages, means standard deviations (and medians and interquartile ranges as appropriate), and ranges in descriptive analyses. We will use paired t-test for comparison of means for normally distributed outcomes and the Wilcoxon Signed Rank test for comparisons of medians on non-normally distributed outcomes. In a secondary analysis we will look for any period effect and any interaction between treatment and period, although no such interaction is predicted and there is probably insufficient power to identify a small interaction. We may, in exploratory analyses, also stratify subjects for secondary analyses of the pre-specified endpoints by the following characteristics: sex, age, usual care insulin total daily dose, body mass index, baseline A1c, and use of CGM in usual care.

VI. c. Power Analysis

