As this study is exploratory in nature, no formal power analysis has been performed. From our insulin specific data collected in our previous study, we identified 7 out of 22 had a difference in t_{max} , 6 out of 22 had a difference in $t_{1/2max}$ and 14 out of 22 had a difference in terminal half-life. We'd like to recruit all 22 of these subjects to participate in this study. Given the occurrence rate of different PK profiles, we believe this will still capture significant information. The sample size of 4 for the Test Run period is a convenience sample with no statistical implications.

We previously showed in a multicenter, outpatient, random-order crossover trial (n=39, 11 days each arm) that the bionic pancreas (BP) reduced group mean CGM glucose (141 ± 10 vs. 162 ± 29 mg/dl, $p < 0.0001$) and percent of time spent <60 mg/dl (0.6 ± 0.6 vs. $1.9 \pm 1.7\%$, $p < 0.0001$) relative to usual care (UC) with pump \pm CGM (El-Khatib FH, et al. Lancet. 2017; 389:369–80). We applied a statistical approach to these data that we will use in this study for comparisons within subjects to determine how many individuals saw benefit for each outcome. We compared the average CGM glucose and average time <60 mg/dl between the BP and UC arms for each patient using autoregressive time series models to determine significance of differences. We found that 72% of subjects had a statistically significant reduction in mean CGM glucose, 51% had significant reduction in time <60 mg/dl, 44% had a significant reduction in both, and 97% had a significant reduction in at least one outcome. These analyses provide a new prospective on the efficacy of the BP emphasizing the benefit to individuals rather than the group as a whole. Subjects least likely to benefit were those who had extremely tight glycemic control and minimal hypoglycemia under UC.

VII. Risks and Discomforts

Subjects may experience mild discomfort associated with the insertion of the infusion set and the Dexcom sensor into the SC tissues. This is expected to be the same as their usual care.

There is a risk of hypoglycemia. This risk is expected to be less than the risk during the subjects' lives outside the trial based on data from earlier trials. All of our previous studies have shown that hypoglycemia is significantly reduced in all configurations of the bionic pancreas when compared with usual care. Based on our experience,

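### The group comparison of mean CGM glucose in this three-period crossover has no period term; adjusting for period costs almost nothing and protects precision, and protects against bias if orders or lost arms are unbalanced

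*Combined protocol and SAP*

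**What the plan says.** Section VI.b plans three pairwise comparisons between arms. The methods paragraph that closes VI.b.3 gives the tests: "We will use paired t-test for comparison of means for normally distributed outcomes and the Wilcoxon Signed Rank test", the latter for non-normal outcomes. On period it says: "In a secondary analysis we will look for any period effect and any interaction between treatment and period". It adds that no interaction is predicted and that power to detect a small one is probably lacking. It does not say what happens to the reported contrasts if a period effect is found.

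On incomplete data the same paragraph says: "In cases where an arm was not completed we will use the available data from that arm in the data analysis". Section IV.a allows for "the possibility that some experiments may have to be discontinued before completion".

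Section V.d.ii says that "subjects will be randomized to one of the possible three visit orders". It does not list the orders. Three insulins have six possible orders, so the phrase may mean three chosen orders, or orders of three visits.

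Under V.d.v (Day 7/Day 1 Visits) the next arm may start the same day or up to 14 days later, and "The memory of the BP will be wiped and it will be re-initialized for the next study period".

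Section VI.b also says: "Statistical comparisons will be made between insulin analogs within a single participant". Section VI.c describes autoregressive time series models for these individual comparisons and states that no formal power analysis was done.

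**The concern.** In a crossover each paired difference contains the insulin difference plus the difference between the two periods in which those insulins were used. When every pair of insulins is balanced over periods, the period part averages to zero. It still adds spread to the differences, so the paired test's standard error is too large. When the pairs are not balanced, part of the drift stays in the estimate.

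The three periods last at least 3 × 7 = 21 days and at most 21 + 2 × 14 = 49 days. At most 30 participants complete them, and the result is meant to inform which insulin suits the device best. With so few participants, precision should not be lost where wording can keep it, and the choice of insulin should not depend on how the orders happen to fall.

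The individual comparisons have a different limit. Each participant takes each insulin in one period only, so within one person insulin and period cannot be told apart by any model. The plan does not say so.

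**Working it through.** The plan gives no power figure to reproduce.

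**Inputs.** n = 30 completers (II, Aim 1). SD of mean CGM glucose on the device 10 mg/dl, from an earlier trial with 11-day arms (VI.c: "reduced group mean CGM glucose (141 ± 10 vs. 162 ± 29 mg/dl"). Assumed, because the documents do not give them: between-arm correlation 0.5, true difference 5 mg/dl, two-sided 5% level, linear drift of d mg/dl per period.

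**SD of paired differences.** 10 × √(2 × (1 − 0.5)) = 10 mg/dl. With correlation 0.8 it is 10 × √0.4 = 6.3.

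**Balanced orders.** For any pair of insulins, the six orders give period differences of ±1 (four orders) and ±2 (two orders). The mean is 0 and the mean square is (4 × 1 + 2 × 4)/6 = 2. A Latin square gives the same mean square. Drift therefore multiplies the paired standard error by k = √(1 + 2d²/SD²).
- SD 10: k = √1.08 = 1.039 at d = 2, and √1.32 = 1.149 at d = 4.
- SD 6.3: k = √1.20 = 1.096 at d = 2, and √1.81 = 1.344 at d = 4.

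**Power by approximation.** SE = 10/√30 = 1.826 and 5/1.826 = 2.739. The paired test has 29 df (t = 2.045), and paired differences adjusted for period have 27 df (t = 2.052).
- Paired: Φ(2.739 − 2.045k) = 75.6% at d = 0, 73.0% at d = 2, 65.1% at d = 4.
- Adjusted: Φ(2.739 − 2.052) = 75.4% at any d.

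**Power by simulation** (six orders × 5):

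| Drift per period | Paired | Period-adjusted differences |
|---|---|---|
| 0 | 74.0% | 73.7% |
| 2 | 72.7% | 75.3% |
| 4 | 65.4% | 75.5% |

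Type I error of the adjusted analysis is near 5%. That of the paired test falls from 4.8% at d = 0 to 4.0% at d = 2 and 2.5% at d = 4, so it is conservative. Without drift the adjusted interval is 0.3% wider (2.052/2.045).

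**Which covariance.** BC222 is a lispro formulation (V.b), so lispro and BC222 may correlate more with each other than with aspart. Take assumed correlations of 0.6 for that pair and 0.4 otherwise. Power for BC222 versus lispro is then:
- Random intercept with residual variance by insulin, no drift: 79.9%, against 84.8% for the paired test. This model loses about 5 points.
- Unstructured covariance: 84.9% at d = 0, 2 and 3, against 85.1%, 82.0% and 78.5% for the paired test.
- Period-adjusted paired differences: 82.9% against 83.3% at d = 0, and 84.4% against 77.8% at d = 3.

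With equal correlations of 0.5 and no drift, the unstructured model gives 75.4% against 75.5%.

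**Unbalanced orders.** Of the 20 ways to choose three orders from six, two are Latin squares with no shift. In 12 the largest shift of a contrast is 0.67d, and in 6 it is 1.33d. For example, with orders ABC, ACB and BAC, the A minus C period differences are −2, −1 and −1, with mean −1.33. This is a count of sets, not a probability.

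**Arms with no data.** Assume six third arms are missing.
- One per order: 26 pairs remain per contrast and there is no bias. At correlations 0.6/0.4 without drift, power is 78.4% paired and 80.9% with the unstructured model.
- All six in the two orders ending in C, three in each: the A minus C differences lost sum to 3 × (−2) + 3 × (−1) = −9. The remaining 24 pairs are then off by 9/24 = 0.375d, or 0.75 mg/dl at d = 2.

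**The case against.** The strongest reply is that nothing in the documents shows drift. All arms use the same automated device, its memory is wiped between arms, and participants are asked to keep diet and exercise similar (V.d.iii). The study calls itself exploratory, and paired tests with a secondary look at period are valid for that purpose. This stands as far as size goes: the gain is modest and could be nil. It is not a reason to leave period out, because the adjustment costs almost nothing and the plan itself regards a period effect as worth examining.

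A second objection is that the usual mixed model can do harm. That also stands for a random intercept with variance by insulin, which forces one common covariance. It does not apply to an unstructured covariance or to period-adjusted paired differences.

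A reader might infer more than the documents support:
- That period is ignored. It is not; a secondary analysis is planned.
- That the paired results are invalid or biased. With balanced orders and complete arms they are unbiased and slightly conservative.
- That three visit orders means unbalanced orders. The text may mean a Latin square, or orders of three visits.
- That incomplete arms are discarded. Partial arms are kept, so the lost-arm gain concerns only arms with no data. The uneven-loss pattern worked above is an illustration without support in the documents.

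**Conclusion.** The point holds as a low-cost improvement that should be made, not as an error that invalidates the plan. The main group comparison of mean CGM glucose has no period term, and the secondary look at period has no stated consequence.

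With balanced orders and complete arms the only loss is precision: nil without drift, about 3 points of power at 2 mg/dl per period and about 10 at 4. Bias needs drift together with either unbalanced orders or uneven loss of whole arms. It is then 0.67 or 1.33 times the drift per period for three-order sets that are not a Latin square, and 0.375 times it in the uneven-loss example.

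These sizes rest on the assumed drift, correlation and true difference, and on an SD borrowed from an earlier trial. They concern mean CGM glucose only, not the skewed time below 54 mg/dl. The limit on comparisons within one participant holds whatever the drift, and the proposed model does not cure it.

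**What to change.** **VI.b.** Make the main group analysis of mean CGM glucose a linear mixed model with insulin and period as fixed effects and an unstructured within-participant covariance across the three insulins. Fit it by REML with Satterthwaite or Kenward-Roger degrees of freedom, and include every participant with data from any arm. Take the three insulin contrasts from it. If it does not converge, use paired differences adjusted for period. Keep the unadjusted paired tests as a sensitivity analysis, and keep the Wilcoxon signed rank test for time below 54 mg/dl.

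**V.d.ii.** Name the orders and make them period-balanced: all six, or a Latin square.

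**Individual comparisons (VI.b, VI.c).** State that within one participant insulin and period cannot be separated, and report those results with that limit.

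**Cost.** Analysis wording and a randomization list, with no added visits or participants. Statistically the price is two degrees of freedom for period and a few more covariance parameters (three variances and three covariances in all). In the simulations with an unstructured covariance the loss without drift was at most 0.6 points of power on any contrast.
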